4.1 Effectiveness Endpoints

Primary Endpoint

The primary endpoint is distance visual acuity (VA) with study lenses, collected in logMAR, for each eye.

[REDACTED]

[REDACTED]

[REDACTED]

■ [REDACTED]

■ [REDACTED]

■ [REDACTED]

■ [REDACTED]

- [REDACTED]
- [REDACTED]
- [REDACTED]
- [REDACTED]
- [REDACTED]
- [REDACTED]
- [REDACTED]
- [REDACTED]
- [REDACTED]
- [REDACTED]
- [REDACTED]
- [REDACTED]

4.2 Effectiveness Hypotheses

Primary Effectiveness

No inferences are to be made on the primary effectiveness endpoint; therefore, no hypotheses are formulated.

[REDACTED]

[REDACTED]

[REDACTED]

4.3 Statistical Methods for Effectiveness Analyses

4.3.1 Primary Effectiveness Analyses

Descriptive statistics will be presented.

[REDACTED]

[REDACTED]

[REDACTED]

[REDACTED]

4.4 Multiplicity Strategy

No multiplicity adjustment needs to be considered for the effectiveness endpoints since no formal hypothesis testing will be conducted.

[REDACTED]

[REDACTED]

[REDACTED]

- [REDACTED]
- [REDACTED]
- [REDACTED]
- [REDACTED]
- [REDACTED]
- [REDACTED]
- [REDACTED]
- [REDACTED]

[REDACTED]

[REDACTED]

5 Safety Analysis Strategy

The focus of the safety analysis will be a comprehensive descriptive assessment of occurrence of adverse events as well as the other listed parameters. Therefore, no inferential testing will be done for the safety analysis.

Part A and Part B will be summarized and presented separately.

5.1 Safety Endpoints

The safety endpoints are

- Adverse events (AE)
- Biomicroscopy Findings/Slit Lamp Examinations

- [REDACTED]

- Device deficiencies

5.2 Safety Hypotheses

There are no formal safety hypotheses in this study. The focus of the safety analysis will be a comprehensive descriptive assessment of safety endpoints listed in Section 5.1.

5.3 Statistical Methods for Safety Analyses

The analysis set for all safety analyses is defined in Section 2.1. Baseline will be defined as the last measurement prior to exposure to study lenses on Visit 1. Safety variables will be summarized descriptively.

5.3.1 Adverse Events

The applicable definition of an AE is in the study protocol. All AEs occurring from when a subject signs informed consent to when a subject exits the study will be accounted for in the reporting.

Pre-treatment AEs will be separated from treatment-emergent AEs occurring during the study period. A pre-treatment AE is an event that occurs after signing informed consent but prior to exposure to study lenses. The period for treatment-emergent AE analysis starts from exposure to study lenses until the subject completes or is discontinued from the study. Each AE will be summarized under the exposed lens based upon the event onset date/time, up until the start of the next lens in the crossover sequence.

The following tables and supportive listings will be provided:

- Incidence of All Ocular Treatment-Emergent Adverse Events
- Incidence of All Nonocular Treatment-Emergent Adverse Events
- Listing of All Ocular Treatment-Emergent Adverse Events
- Listing of All Nonocular Treatment-Emergent Adverse Events
- Listing of All Ocular Pre-Treatment Adverse Events
- Listing of All Nonocular Pre-Treatment Adverse Events

5.3.2 Biomicroscopy Findings/Slit Lamp Examination

The following tables and supportive listings will be provided:

- Frequency and Percentage for Biomicroscopy Findings by Visit
- Incidence of Increased Severity by 2 or More Grades in Biomicroscopy Findings
- Listing of Subjects With Other Biomicroscopy Findings
- Listing of Subjects With Increased Severity by 1 Grade in Biomicroscopy Findings
- Listing of Subjects With Increased Severity by 2 or More Grades in Biomicroscopy Findings
- Listing of Subjects with Infiltrates

5.3.3 Device Deficiencies

The following tables and supportive listings will be provided:

- Frequency of Treatment-Emergent Device Deficiencies
- Listing of Treatment-Emergent Device Deficiencies
- Listing of Device Deficiencies Prior To Treatment Exposure

6 Analysis Strategy for Other Endpoints

[figure not shown]
Not applicable.

7 Sample Size and Power Calculations

No formal sample size calculation is provided given the descriptive and pilot nature of the study.

8 References

Not applicable.

10 Appendix

[figure not shown]
Table 10-1 Schedule of Study Procedures and Assessments – Part A

Procedure/ Assessment	PRESCREENING	LENS 1				LENS 2		USV
		Visit 1 Screen/ Baseline/ Dispense Lens 1	Visit 2 Day 15 Follow- up Lens 1	Visit 3 Day 30 Follow-up Lens 1 Dispense Lens 2		Visit 4 Day 15 Follow- up Lens 2	Visit 5 Day 30 Follow- up Lens 2 /Exit^	
				Follow-up Lens 1	Dispense Lens 2			
Informed Consent		X						
Demographics		X						
Medical History*		X	X	X	X	X	X	X
Concomitant Medications*		X	X	X	X	X	X	X
Inclusion/ Exclusion		X						
Habitual (lens brand, lens power*, lens care)		X						
VA w/ habitual correction* (OD, OS, Snellen distance)		X					X	(X)
Manifest Refraction and BCVA with manifest refraction* (OD, OS, Snellen distance)		X	(X)	(X)	(X)	(X)	(X)	(X)
Biomicroscopy		X	X	X		X	X	X
████████████████████	█	█						
████████████████████		█	█	█	█	█	█	█
████████								
Randomization and record lens power*		X						
Dispense study lenses		X	(X) ^Ω		X	(X) ^Ω		(X)
VA w/ study lenses (OD, OS, logMAR distance)		X	X	X	X	X	X	(X)

USV = Unscheduled visit

[REDACTED]

Signature Page for V-CLN-0001221 v3.0

Signature Page for V-CLN-0001221 v3.0

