1 PROTOCOL SYNOPSIS

Trial Sponsor	Alcon Research, LLC [name]
Name of Test Product(s)	LID018869
Name of Control Product(s)	Control Product 1 (Part A): ACUVUE OASYS® with HYDRACLEAR® PLUS (AOHP) Control Product 2 (Part B): CooperVision® Biofinity® (Biofinity)
Title of Trial	Clinical Comparison of Two Daily Wear Frequent Replacement Silicone Hydrogel Soft Contact Lenses
Protocol Number	CLY935-C020
Number of Sites	~4
Country	US
Planned Duration of Exposure – Part A	~60 days total duration (test and control): Test Product: ~30 days Control Product 1: ~ 30 days (2x ~15 days)
Planned Duration of Exposure – Part B	~30 days total duration (control only) Control Product 2: ~ 30 days
Number of Subjects – Part A	Target to complete: 60 (~30 per each parallel group)
	Planned to enroll: ~66
Number of Subjects – Part B	Target to complete: 60 (~ 30 per each parallel group)
	Planned to enroll: ~66
Study Population	Volunteer subjects aged 18 or over who are habitual spherical [REDACTED] soft contact lens wearers, have at least 3 months of contact lens wearing experience, and who wear their habitual lenses at least 5 days per week and at least 10 hours per day. [REDACTED] [REDACTED] [REDACTED] [REDACTED] [REDACTED] [REDACTED] [REDACTED]

	
[REDACTED]

Objective(s)	
The primary objective of this study is to evaluate the overall performance of an investigational silicone hydrogel lens when compared to AOHP.
 
[REDACTED]
 
[REDACTED]
 
[REDACTED]

Endpoints	
Primary Effectiveness
 
Distance VA (logMAR) with study lenses 
[REDACTED]
 
[REDACTED][REDACTED][REDACTED][REDACTED][REDACTED][REDACTED][REDACTED][REDACTED][REDACTED][REDACTED][REDACTED][REDACTED][REDACTED][REDACTED] 
Safety
 
AEsBiomicroscopy findingsDevice deficiencies
Assessments	
Effectiveness
 
Distance VA (logMAR) with study lensesDistance VA (Snellen) habitual correctionManifest refractionBCVA (Snellen distance with manifest refraction) 
[REDACTED]
 
[REDACTED]
 
[REDACTED]
 
[REDACTED]

	
 • [REDACTED] ■ [REDACTED] 
Safety
 
 • AEs • Biomicroscopy • Device deficiencies 	

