3.3 Risks and Benefits

Contact lenses may offer improved peripheral vision and the convenience of not wearing spectacles. Material properties and design characteristics of the contact lens in development are features consistent with successful contact lens wear.

[REDACTED]

[REDACTED]

[REDACTED]

[REDACTED]

AOHP contact lenses are commercially available for daily wear use under a biweekly replacement schedule; Biofinity contact lenses are commercially available for daily wear use under a monthly replacement schedule; further details on any known potential risks and benefits can be found in the package insert. Refer to Appendix 13.1 and Appendix 13.2.

The site personnel will educate subjects on proper hygiene and lens handling, and compliance with the use of contact lenses according to the protocol. Subjects should be instructed not to wear contact lenses while sleeping or swimming. The site personnel will also advise the subjects to remove contact lenses and return for prompt follow-up of symptoms, such as ocular discomfort, foreign body sensation, excessive tearing, vision changes, or hyperemia.

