1.2 Study Description

Key components of the study are summarized in Table 1-1.

Table 1-1 Study Description Summary

Study Design – Part A	Prospective, randomized, parallel group, crossover, double-masked, bilateral, [REDACTED]
Study Design – Part B	Prospective, single group [REDACTED] single-masked, bilateral
Study Population	Volunteer subjects aged 18 or over who are habitual spherical weekly/monthly soft contact lens wearers, have at least 3 months of contact lens wearing experience, and who wear their habitual lenses at least 5 days per week and at least 10 hours per day. [REDACTED] [REDACTED] [REDACTED] [REDACTED] [REDACTED] [REDACTED] [REDACTED] [REDACTED]

	
Number of Subjects – Part A Target to complete: 60 (~30 per each parallel group) Planned to enroll: ~66
 
Number of Subjects – Part B Target to complete: 60 (~30 per each parallel group) Planned to enroll: ~66

Number of Sites	~4 US
Test Product	LID018869
Control Product	Control Product 1 (Part A): ACUVUE OASYS® with HYDRACLEAR® PLUS (AOHP) Control Product 2 (Part B): CooperVision® Biofinity® (Biofinity)
Planned Duration of Exposure – Part A	~60 days total duration (test and control): Test Product: ~30 days Control Product 1: ~30 days (2x ~15 days)
Planned Duration of Exposure – Part B	~30 days total duration (control only): Control Product 2: ~30 days
Visits – Part A	
Pre-Screening*
 
Visit 1: Screen/Baseline/Dispense Lens 1
 
Visit 2: Day 15 Follow-up Lens 1 [REDACTED]
 
Visit 3: Day 30 Follow-up Lens 1/Dispense Lens 2 [REDACTED]
 
[REDACTED]
 
Visit 4: Day 15 Follow-up Lens 2 [REDACTED]
 
Visit 5: Day 30 Follow-up Lens 2/Exit [REDACTED]
 
*Optional

Visits – Part B	
Pre-Screening*
 
Visit 1: Screen/Baseline/Dispense Lens 1
 
Visit 2: Day 15 Follow-up Lens 1 [REDACTED]
 
Visit 3: Day 30 Follow-up Lens 1/Exit [REDACTED]
 
*Optional

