2.1 Safety Analysis Set

Safety analyses will be conducted using the safety analysis set on a treatment-emergent basis. As such, the safety analysis set will include all subjects/eyes exposed to any study lenses evaluated in this study. For treatment-emergent safety analyses, subjects/eyes will be categorized under the actual study lenses exposed in the corresponding lens sequence.

Adverse events occurring from the time of informed consent but prior to first exposure to study lenses will be summarized in subject listings.

3 Subject Characteristics and Study Conduct Summaries

The following tables will be presented for Part A [by lens Sequence or by Lens] and Part B separately:

- Subject Disposition [by Lens Sequence]
- Analysis Set [by Lens]
- Analysis Set [by Lens Sequence]
- Subject Accounting [by Lens Sequence]
- Demographics Characteristics [by Lens Sequence]

- Baseline Characteristics [by Lens Sequence] (habitual lens brand, habitual lens care brand, [REDACTED])

In addition, the following subject listings will be provided for Part A and Part B separately:

- Listing of Subjects Excluded from Protocol Defined Analysis Set
- Listing of Lens Sequence Assignment by Investigator
- Listing of Subjects Discontinued from Study

4 Effectiveness Analysis Strategy

This study defines one primary endpoint [REDACTED]. The Safety Analysis Set will be used for all effectiveness analyses.

Part A and Part B will be summarized and presented separately.

Continuous variables will be summarized using the number of observations, mean, standard deviation, median, minimum, and maximum. Categorical variables will be summarized with counts and percentages from each category.

All data obtained in evaluable subjects/eyes will be included in the analysis. No imputation for missing values will be carried out for the primary analysis.

A listing of select effectiveness data will also be provided.

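### Part A is expected to use about four AOHP lenses per subject against an inferred two test lenses, but the device deficiency table states no unit and has no per-lens denominator

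*SAP*

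**What the plan says.** SAP 5.3.3 plans one table, "Frequency of Treatment-Emergent Device Deficiencies", with a listing of the same events and a separate listing of deficiencies that precede treatment exposure. It does not say whether the table counts events, eyes or subjects, and names no denominator.

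SAP 5.3 refers all safety analyses to the set in SAP 2.1, where "the safety analysis set will include all subjects/eyes exposed to any study lenses evaluated in this study". This points to subjects/eyes as the implied base, but 5.3.3 does not say so.

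On lens use in Part A, the Protocol synopsis gives "Test Product: ~30 days" for the test lens and "Control Product 1: ~ 30 days (2x ~15 days") for AOHP; SAP Table 1-1 agrees. Protocol 3.3 explains the split: "AOHP contact lenses are commercially available for daily wear use under a biweekly replacement schedule". The Part A schedule (Protocol Table 1-1, SAP Table 10-1) has a conditional, footnoted dispensing mark at Visits 2 and 4, the Day 15 visit of each lens period. The footnote is redacted.

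**The concern.** Many deficiencies attach to the individual lens: a wrong label, a faulty package, a manufacturing flaw. The opportunity for these grows with the number of lenses opened, not with the number of subjects. Because Part A is a crossover, nearly the same subjects and eyes appear under both products, while the number of lenses opened probably differs by a factor of two. A table of counts, or of percentages of subjects or eyes, would then tend to show more deficiencies for AOHP even if the two lenses were equally well made.

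Device deficiencies are a named safety endpoint, and the primary objective is performance compared with AOHP. With no test or model planned, the displayed figures are what a reader will compare, and for once-per-lens faults the distortion runs in one direction, in favor of the test lens.

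**Working it through.** **Inputs from the documents**

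- Wear in Part A: test about 30 days; AOHP 2 x about 15 days (Protocol synopsis, SAP Table 1-1).
- Bilateral wear, crossover, 1:1 randomization to sequence (SAP 1.2 and 1.3).
- Target to complete: 60, about 30 per sequence (SAP Table 1-1).

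**Assumptions**

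- One test pair per subject. This is inferred from the unsplit 30 days; no readable text gives the number of pairs.
- The same deficiency probability p per lens for both products. The documents give no rate, so a range is shown.

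**The plan's own figure.** 30 + 2 x 15 = 60 days, which reproduces the stated "60 days total duration (test and control"). There is no sample size or power figure to reproduce.

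**Lenses per product**

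- Per subject: test 1 pair x 2 eyes = 2; AOHP 2 pairs x 2 eyes = 4.
- For 60 subjects: test 60 x 2 = 120; AOHP 60 x 4 = 240.

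**Once-per-lens deficiencies at equal quality**

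- Expected events = lenses x p.
- Share of eyes with at least one: test p; AOHP 1-(1-p)^2.
- Share of subjects with at least one: test 1-(1-p)^2; AOHP 1-(1-p)^4.

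| Assumed p | Events, test v AOHP | Event ratio | Eye ratio | Subjects, test v AOHP | Subject ratio |
|---|---|---|---|---|---|
| 1% | 1.2 v 2.4 | 2.0 | 1.99 | 1.99% v 3.94% | 1.98 |
| 5% | 6 v 12 | 2.0 | 1.95 | 9.75% v 18.55% | 1.90 |
| 10% | 12 v 24 | 2.0 | 1.90 | 19.0% v 34.39% | 1.81 |

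The choice among events, eyes and subjects therefore hardly matters at low p. Per lens, the two products agree: at p = 1%, 1.2/120 = 2.4/240 = 1.0%.

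**Mixed causes.** Wear time is the same for both products (about 30 days), so deficiencies that build up with wear should not double. If a share w of test-lens deficiencies scales with lenses opened and the rest with wear days, the ratio is 2w + (1-w) = 1 + w: 1.25, 1.5 and 1.75 for w = 25%, 50% and 75%.

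**Deficiencies found before insertion.** SAP 5.3.3 sends pre-exposure deficiencies to a listing, but does not say whether exposure means the first study lens of any kind or the first of each product. Take the first reading, with 30 subjects per sequence. The first pair in each sequence then drops out of the table.

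- Test first: 0 test lenses and 30 x 4 = 120 AOHP lenses remain.
- AOHP first: 30 x 2 = 60 test lenses and 30 x 2 = 60 AOHP lenses remain.
- Total: 60 test v 180 AOHP openings, a ratio of 3.

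**Chance variation.** With independent binomial counts on 120 and 240 lenses at p = 1%, AOHP's count is no higher than the test lens's with probability 0.36.

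**The case against.** The SAP does not say that the table is over subjects/eyes. The neighboring biomicroscopy section asks for frequency and percentage, and other tables are titled as incidence, so frequency alone may mean a plain count. This stands as a limit on what can be claimed: the gap is an unstated unit, not a demonstrably wrong denominator. It does not remove the problem, since a plain count gives the full ratio of 2.0.

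The protocol's definition of a device deficiency also covers durability, performance and use errors, many of which can accrue with wear or handling, so an overall ratio of two is not established. Nor is it settled which pre-insertion faults the table would include. Both points stand.

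Deficiencies per wearer over about 30 days, with each product on its own schedule, is a legitimate description, and per-lens quality is a supplementary question. That is right, and it is why the planned summary should be kept. The planned listing and the disclosed wear schedule also allow an attentive reader to see the imbalance, though not to count the lenses.

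A reader might infer that the table will make the test lens look superior, or that the plan is biased toward the sponsor's product. The documents do not support that. No rate is given, and at p = 1% the expected difference is 1.2 events. There is no success criterion (SAP Executive Summary) and no safety hypothesis (SAP 5.2), and the number of test pairs is itself an inference.

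**Conclusion.** The point holds in a limited form. The readable text supports about twice as many AOHP as test lenses per subject, and SAP 5.3.3 has neither a stated unit nor a lens denominator. For deficiencies that arise once per lens, equal quality would appear as roughly 2:1 against AOHP on any of the available counts. For all deficiencies together the ratio lies between 1 and 2, depending on how many build up with wear, and it could reach 3 for those found before insertion under one reading of treatment exposure.

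This rests on one test pair per subject, Day 15 replacement of AOHP in all subjects, and equal p. The effect is on descriptive interpretation only, so the priority is minor. It is still worth correcting, because the distortion of once-per-lens faults has a predictable direction on a named safety endpoint in a comparative study.

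**What to change.** In SAP 5.3.3:

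1. State the unit counted (events, eyes or subjects).
2. State how treatment exposure applies to deficiencies in each lens period, including those found before a replacement pair or the second product is inserted. SAP 5.3.1 already sets such a rule for adverse events.
3. Show the number of lenses dispensed per product, including Day 15 and unscheduled replacements.
4. Report deficiencies per lens dispensed beside the planned summary, which stays.

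The cost is a few lines of SAP text and one denominator per product. That denominator is expected to come from dispensing and accountability records: dispensing is a scheduled procedure, and Protocol 4.3 requires all study products to be accounted for. Most of the accountability text is redacted, so the sponsor should confirm that lens counts by product can be extracted.
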